## 14.3 Subject Informed Consent

Prior to participation, all subjects must confirm their free and voluntary willingness to participate in the study. This confirmation is obtained in writing after having received a full oral and written explanation on the study:

- Aims, methodology and duration of the study;
- Potential benefits, foreseeable risks and inconveniences related to the study;
- Rights and responsibilities of subjects, with particular emphasis on the right to refuse study participation or to withdraw consent to participation at any time without consequences or penalties;
- Information on IMP and its administration;
- Contact details of persons dedicated to the study at the investigational site.

The language used when informing the subjects and answering their questions must be as understandable as possible and shall not induce any misunderstanding or feeling to be influenced to participate. Subjects must be given ample time to decide whether they agree to participate or not.

Subjects may consent to participate after having received all necessary information and all satisfactory answers to their questions. Their consent must be confirmed in writing by dating and signing the informed consent form(s) approved by the corresponding IRB/IEC.

 CONFIDENTIAL	Protocol No. GDX-44-004 Version No. 2.0 (Protocol including amendment n°1) Date: 11 July , 2016	 Page 70 / 84
---------------------------------------------------------------------------------------------------	----------------------------------------------------------------------------------------------------------	-----------------------------------------------------------------------------------------------------

When the consent may not be directly obtained in writing, a legal representative/impartial witness may be involved in the process and confirm in writing that the subject consented freely and voluntarily, according to local regulation.

The information of subjects may only be conducted by qualified investigational site personnel, whose involvement and responsibility for subject information has been fully documented and approved by the Principal Investigator.

The Principal Investigator must ensure that local applicable regulations/requirements are fully observed by the staff under her/his responsibility.

In case of modifications of the subject informed consent form or of any other document to be provided to the subjects and approved by the Sponsor, the IRB/IEC approval must be obtained prior to implementing the new document(s). Subjects who already consented may be asked to confirm their willingness to continue participating in writing. In any case, the same information and consent process as described above must be followed.

#### 14.4 Study Records and Archiving

During the course of the clinical study, investigational sites must ensure completeness and accuracy of the study records that are to be filed in the ISF provided by Guerbet at the initiation visit. The completeness and accuracy of such files will be checked regularly by Guerbet representative (Clinical Research Associate or Monitor). The final check will occur at the close out visit when investigational site participation is over.

At the end of the study, investigational sites must ensure the ISF will be archived in an appropriate way that allows timely access and proper retention of documents. Retention period will be of at least 15 years after study completion. Guerbet will notify the investigational sites in writing when study documents are no longer needed for retention.

 CONFIDENTIAL	Protocol No. GDX-44-004 Version No. 2.0 (Protocol including amendment n°1) Date: 11 July , 2016	 Page 71 / 84
----------------------------------------------------------------------------------------------------------	----------------------------------------------------------------------------------------------------------	-----------------------------------------------------------------------------------------------------

## 15 QUALITY CONTROL / QUALITY ASSURANCE

### 15.1 Direct Access to Source Data/Documents

The investigator will allow Guerbet representatives, the persons responsible for audit conduct, the representatives of the Ethics Committees and of the Regulatory Authorities to have direct access to source data/documents.

The investigator must guarantee the safety of the study data in the medical files by implementing security measures to prevent unauthorised access to the data.

The investigator undertakes, in accordance with the regulation in force, to make anonymous any subject data before collection by Guerbet. Especially the name and address of the subjects will not be captured by any medium such as document for biological results, digital supports, ECG tracings etc...

For this study, the following will be considered as source data (as a minimum): subjects medical files, images.

If computerised medical files are used, the investigator must:

- At the start of the study, print, sign and date all the medical files of all subjects,
- During the study, print, sign and date in real time each data entry and each data change,
- In case printing of files is not possible, the computerized system must be validated and access should be granted to Guerbet or its representative.

### 15.2 Clinical Monitoring

Before the study is conducted at a given investigational site and until the study is completed/ terminated at the same given investigational site, Guerbet will mandate a representative to perform a close monitoring of the study conduct that will ensure that the investigational site is properly equipped; the staff is adequately experienced and knowledgeable of regulatory and ethical requirements.

The representative will perform regular investigational site visits and report all discussions, subject and IMP data verification performed with particular attention to subjects' safety, well-being and study data accuracy and completeness.

A representative in charge of monitoring of blinded data and another one in charge of unblinded data review will be involved in the clinical monitoring of the study.

### 15.3 Clinical Data Handling

#### 15.3.1 Data Reported in the eCRF

The eCRF will allow recording of the data required by the protocol.

The investigator or the designated person from his/her team agrees to complete the eCRF, at each subject visit, and all other documents provided by Guerbet (e.g.; documents relating to the IMP management) and to reply to any raised data clarifications in a timely manner.

The investigator must attest:

- The authenticity of the data collected in the eCRF;

 CONFIDENTIAL	Protocol No. GDX-44-004 Version No. 2.0 (Protocol including amendment n°1) Date: 11 July , 2016	 Page 72 / 84
---------------------------------------------------------------------------------------------------	----------------------------------------------------------------------------------------------------------	-----------------------------------------------------------------------------------------------------

- The consistence between the data in the eCRF and those in the source documents

### ***15.3.2 Data Reported in the eCRF according to Subject Status***

For screening failure, only the date of visit, date of informed consent signature, demographic data, the adverse event and the reason for non-selection will be reported.

For included subjects, withdrawn before the administration of the IMP, only the selection data, the safety data and the reason for withdrawal will be reported.

For subjects withdrawn from the study after the administration of the IMP, all data available at the time of withdrawal will be reported in the medical file and the eCRF (e.g.: inclusion data, safety data, administration data, imaging data, reason for withdrawal...). The investigator must make every effort to collect and record all follow-up safety information (i.e. adverse events, injection-site tolerance, as appropriate), unless the subject withdraws consent for further data collection/participation for/in the study.

### ***15.3.3 Data Management System***

A validated clinical data management system will be used for data process and data storage.

Data processing and control will be closely managed by Guerbet.

## **15.4 Audits and Inspections**

[figure not shown]
At any time during the study conduct, Guerbet may mandate a representative to perform an audit of investigational sites in order to assess compliance with the regulatory and ethical requirements, the study protocol and related instructions and to assess the accuracy and completeness of data generated by the investigational sites.

In parallel, at any time during the study conduct Regulatory/Competent/ Authorities may also carry out an inspection in the facilities of Guerbet and/or the investigational sites. Guerbet will inform all the investigators immediately upon notification of a pending inspection. Likewise, the investigator will inform Guerbet of any pending inspection.

Whether for an audit or for a regulatory inspection, Guerbet and the investigational sites both agree to cooperate in full transparency, confidentiality and professional secrecy.

The investigator must allow the representatives of Guerbet (audit) and/or of the Competent/Regulatory Authorities (inspection):

- To inspect the site, facilities and study material,
- To meet all members of his/her team involved in the study,
- To have direct access to study data and source documents,
- To consult all of the documents relevant to the study.

## 18 COMPANY LIABILITY INSURANCE

Guerbet's liability, as well as the liability of the investigators participating to this study, is covered by an insurance policy, a copy of the certificate being submitted to the investigator.

Furthermore, Guerbet and the investigator undertake to comply with the locally applicable legal requirements with respect to insurance.

However, Guerbet and its insurer reject all liability in the following cases, which are merely indicative and not exhaustive:

- An accident due to a cause other than the investigational medicinal product administered,
- An accident occurring during use of the investigational medicinal product differently from the instructions given in the study protocol,
- An accident occurring for a subject whose consent to participation was not adequately collected.

## 19 APPENDICES

### 19.1 Volume of P03277 injection by dose group and body weight

Adults		Dose (mmol/kg)			
		0.025	0.05	0.1	0.2
		Dose (mL/kg)			
		0.05	0.1	0.2	0.4
Body Weight		Volume (mL)	Volume (mL)	Volume (mL)	Volume (mL)
Kilograms (kg)	Pounds (lb)				
40	88	2	4	8	16
50	110	2,5	5	10	20
60	132	3	6	12	24
70	154	3,5	7	14	28
80	176	4	8	16	32
90	198	4,5	9	18	36
100	220	5	10	20	40
110	242	5,5	11	22	44
120	264	6	12	24	48
130	268	6,5	13	26	52
140	308	7	14	28	56
150	330	7,5	15	30	60

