### 5.1 Investigational Medicinal Product(s)

#### 5.1.1. *Investigational Medicinal Product 1*

Name: P03277 

Pharmaceutical form: vial of 20 ml

P03277 is an aqueous solution. Each vial contains 20 mL of solution presented as a sterile, clear, yellow, ready-to-use solution for injection.

Concentration: 0.5 M

P03277 dose per administration: P03277 will be injected according to randomization at 1 of 4 different doses (1 dose per subject according to allocated randomized arm):

- First subset of subjects: 0.05 or 0.1 mmol/kg BW (corresponding to 0.1 or 0.2 mL/kg body weight) in a 1:1ratio.
- Second subset of subjects: 0.025, 0.05, 0.1 or 0.2 mmol/kg body weight (corresponding to 0.05, 0.1, 0.2 or 0.4 mL/kg body weight) in a 1:1:1:1 ratio.

Sufficient IMP must be allocated to one subject by IWRS.

Route and method of administration: by intravenous (IV) bolus injection at 2 mL/s rate without dilution, followed by a saline flush to ensure complete injection of the contrast medium.

The P03277 administration is preferably performed by power injector in order to better control injection rate, but manual injection is also permitted in case it is necessary.

Please refer to the Investigator Brochure for more information on P03277.

 CONFIDENTIAL	Protocol No. GDX-44-004 Version No. 2.0 (Protocol including amendment n°1) Date: 11 July , 2016	 Page 28 / 84
----------------------------------------------------------------------------------------------------------	----------------------------------------------------------------------------------------------------------	-----------------------------------------------------------------------------------------------------

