**Unenhanced and contrast-enhanced MRI examinations:**

- Unenhanced and contrast-enhanced MRI will be performed according to the required pulse sequences specified in [Section 9.2.2](#).

The appropriate dose/volume of P03277 or MultiHance® (see [Appendices 19.1 and 19.2](#)) will be administered by IV as a bolus at the rate of 2 mL/second using ideally a power injector via a peripheral vein (the antecubital vein is preferred). The IV injection line will consist of a large bore indwelling catheter (at least 18 gauge). P03277 or MultiHance® will be followed by a 0.9% saline flush using ideally a power injector.

The following information will be documented in the source document and reported on the restricted eCRF pages (unblinded staff access): the location of the IV injection line, the injection method (power injector or manual), actual volume injected and actual rate of the injection.

The start time of contrast injection and start time of post injection axial 3D T1 weighted GRE for brain and sagittal T1-weighted SE/TSE for spine, will be recorded. Any deviation from the specified MRI procedures and the reason for it (scanner-related problem or subject-related problem) will be also documented.

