#### 10.1.2 *Recording/Collection of Adverse Events*

The Investigator or his/her designee will invite the subject to report any experienced abnormality as part of the usual clinical follow-up.

All Adverse Events, whether considered as related or not to the Investigational Medicinal Product and/or the imaging procedure should be reported in the medical file and the eCRF and monitored from onset to resolution or stabilization of sequelae. If no follow-up is performed, the investigator must provide a justification in the medical file.

In order to ensure complete safety data collection, all Adverse Events occurring during the time of the subject's participation in the study, must be reported and monitored even if no IMP was administered. The investigator shall document all Adverse Events in the medical file and the appropriate section of the eCRF.

As a reminder the subject's participation is defined as the period from the screening visit (ICF signature) to the last study visit and defined in [Section 11](#) in case of premature discontinuation.

Safety information is to be collected by the investigator with the same procedure as Adverse Events: treatment errors and uses outside what is foreseen in the protocol, including misuse and abuse of the product, suspicion of transmission of an infectious agent via an IMP, overdose (symptomatic or not), all reports of pregnant or breastfeeding women exposure even if uneventful, all reports of suspected drug-drug interaction with another product (symptomatic or not).

As an exception, as the study aims to assess the effective dose of P03277, doses with lesser efficacy are expected and will be considered while analyzing the primary endpoint.

In this protocol, the overdose is defined as more than 0.3 mmol/kg for P03277 and more than 0.2 mmol/kg for MultiHance®. Any overdose, with or without adverse event, will be reported as AE and, in addition, on SAE form if the associated event is serious.

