Subject not withdrawn as per protocol	Stopping rules detected on local measurements and subject not withdrawn: Increase in serum creatinine by more than 25% or 0.5 mg/dL (44 umol/L) compared to the baseline value	Clinical data base	Non major
	Stopping rules detected on central measurements and subject not withdrawn: Increase in serum creatinine by more than 25% or 0.5 mg/dL (44 umol/L) compared to the baseline value	Central laboratory data base	Non major
	Stopping rules detected on central measurements and subject not withdrawn: Increase in cystatin C by more than 25% compared to the baseline value	Central laboratory data base	Non major
	Stopping rules detected on central measurements and subject not withdrawn: triplicate QTc Bazett or QTc Fridericia > 500 ms or in increase of > 60 ms over baseline	Central ECG data base	Non major
	Result of pregnancy test positive and subject not withdrawn	Clinical data base	Non major
Unblinding	Blind not maintained on site	Monitoring	Non major
	Blind not maintained at central reading level	Monitoring	Major
Forbidden concomitant medication	Concomitant medication taken in or medical procedure between the two MRI impacting lesion size based on investigator assessment	Clinical data base	Major
IMP deviation	Subject not allocated in the good stratification factor	Clinical data base and IWRS data base	Non major
	Subject not allocated in the good sequence	Clinical data base and IWRS data base	Major
	Subject having performed MRI examination but not administered with the IMP	Clinical data base	Major
	The IMP volume actually administered is different from the theoretical one from 10 to 20%	Clinical data base and IWRS data base	Non major
	The IMP volume actually administered is different from the theoretical one from more than 20%	Clinical data base and IWRS	Major
	Location of IMP injection site is not adequate	Clinical data base	Non major
	Actual IMP injection rate is not adequate	Clinical data base	Non major
	Temperature excursion for IMP	Monitoring	Non major
	IMP management not appropriate	Monitoring	Non major
	Extravasation	Clinical data base	Major
Missing data	Date of birth is missing	Clinical data base	Non major
	Sex is missing	Clinical data base	Non major
	Height is missing	Clinical data base	Non major
	Race is missing	Clinical data base	Non major
	Physical examination not performed	Clinical data base	Non major

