### 5.3. Measurements of study drug compliance

The subject's theoretical dose of contrast agent calculated for each subject was given by Interactive Web Response System (IWRS). The subject's actual dose administered was recorded in the electronic Case Report Form (eCRF). When the actual dose was different from the theoretical dose, the reason had to be given and recorded in the eCRF. Subjects with a difference between theoretical and actual volumes of study product will be described using the FAS. The difference in mL and in % will be presented for these subjects by descriptive statistics. The reasons of the differences will be listed only.

The table and the listing that will be displayed are detailed in Sections 6.1.1.6 and 6.2.5.

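### Both dosing tables (Protocol Appendices 19.1 and 19.2) print 268 lb beside 130 kg; the tables' own factor of 2.2 gives 286 lb

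*Protocol*

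**What the plan says.** Protocol 9.1.2 (visit 2) and 9.1.4 (visit 4) open the injection instruction with "The appropriate dose/volume of P03277 or MultiHance" and refer to Appendices 19.1 and 19.2. Each appendix has 12 rows, from 40 to 150 kg in steps of 10 kg, with the weight in kilograms, the weight in pounds and the volume to inject.

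In Appendix 19.1 the 130 kg row reads "130 268 6,5 13 26 52": 130 kg, 268 lb, then the volumes in mL for 0.025, 0.05, 0.1 and 0.2 mmol/kg of P03277. The rows on either side read "120 264 6 12 24 48" and "140 308 7 14 28 56". Appendix 19.2 also prints 268 lb beside 130 kg, with 26 mL of MultiHance.

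The volumes rest on rates given elsewhere. Protocol 5.1.1 states the four P03277 doses as "corresponding to 0.05, 0.1, 0.2 or 0.4 mL/kg body weight", and 5.1.2 gives 0.2 mL/kg for MultiHance. Both products are 0.5 M.

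Three other places help to judge the size of the error:

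- Protocol 10.1.2: "the overdose is defined as more than 0.3 mmol/kg for P03277 and more than 0.2 mmol/kg for MultiHance".
- SAP 5.2.2: the smallest volume deviation listed is "The IMP volume actually administered is different from the theoretical one from 10 to 20" per cent, classed as non major. Only a difference above 20% is major.
- SAP 5.3: the IWRS supplied each subject's theoretical dose. "When the actual dose was different from the theoretical dose, the reason had to be given and recorded in the eCRF".

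**The concern.** Going down the pound column, the weight rises by 4 lb from 120 to 130 kg and by 40 lb from 130 to 140 kg, while every other 10 kg step adds 22 lb. The 130 kg entry does not belong to the series.

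These are working dosing tables, cited at both injections. The pound column can only be there for staff who work in pounds. Anyone who finds the row by that column would treat a subject of about 122 kg as weighing 130 kg and inject too much of whichever agent is due. The investigator is blinded to product and dose (Protocol 5.3.2), so the unblinded person preparing the injection would have to notice the error.

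**Working it through.** **Inputs.** Weights and volumes are from Appendices 19.1 and 19.2, rates from Protocol 5.1.1 and 5.1.2, and the concentration is 0.5 M (0.5 mmol/mL). The conversion factor is either 2.2, which is what the tables use, or 2.20462 lb/kg, the exact factor, which the documents do not give and is assumed here.

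**Step 1: the pound column.** Divide pounds by kilograms in each row. From 88/40 to 330/150, 11 of the 12 rows give exactly 2.2, including 264/120 and 308/140. The 130 kg row gives 268/130 = 2.06. The consistent value is 130 x 2.2 = 286 lb. Rounding does not explain the gap, because the exact factor gives 130 x 2.20462 = 286.6 lb. A PDF reading error is unlikely, since the same digits stand in two separate tables.

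**Step 2: the volumes.** Volume = rate x kg reproduces every mL entry in Appendix 19.1. For 130 kg: 0.05 x 130 = 6.5, 0.1 x 130 = 13, 0.2 x 130 = 26 and 0.4 x 130 = 52 mL. For MultiHance, 0.2 x 130 = 26 mL. Only the pound cell is wrong.

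**Step 3: a 268 lb subject read from the 130 kg row.**

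- Factor 2.2: 268/2.2 = 121.82 kg; excess = 130/121.82 - 1 = 6.7%.
- Factor 2.20462: 268/2.20462 = 121.56 kg; excess = 130/121.56 - 1 = 6.9%.

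The correct volume is rate x true weight; the delivered dose is table volume x 0.5 / true weight. Where two values are shown, the first uses factor 2.2 and the second 2.20462.

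| Agent and dose (mmol/kg) | Table (mL) | Correct (mL) | Delivered (mmol/kg) |
|---|---|---|---|
| P03277 0.025 | 6.5 | 6.09 / 6.08 | 0.0267 |
| P03277 0.05 | 13 | 12.18 / 12.16 | 0.0534 / 0.0535 |
| P03277 0.1, or MultiHance 0.1 | 26 | 24.36 / 24.31 | 0.1067 / 0.1069 |
| P03277 0.2 | 52 | 48.73 / 48.63 | 0.2134 / 0.2139 |

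**Step 4: interpolating between rows by pounds.** At 286 lb the printed column gives 130 + 10 x (286 - 268)/(308 - 268) = 134.5 kg, against a true 130 kg: 134.5/130 - 1 = 3.5% too high. At 297 lb it gives 137.25 kg against 135 kg, or 1.7% too high. The error is zero at 264 and 308 lb.

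**Step 5: against the plan's limits.** The highest P03277 dose would be 0.214 mmol/kg against an overdose limit of 0.3, and MultiHance 0.107 against 0.2. The excess of 6.7 to 6.9% is below the 10% at which SAP 5.2.2 starts to list volume deviations.

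**The case against.** The case against giving this weight is strong on consequences, and it does not dispute the arithmetic.

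- The volume has another source. SAP 5.3 says the IWRS supplied each subject's theoretical dose, and SAP 5.6.1.2 lists the theoretical volume per IWRS in mL. The rule is also stated correctly per kilogram in Protocol 5.1.1 and 5.1.2 and at the head of both tables, and nothing in the documents shows weights being entered in pounds.
- The 6.7 to 6.9% is a worst case. It needs a subject near 268 lb and a user who relies on the pound column alone.
- A correct table with 10 kg steps is already coarse. Taking the 50 kg row for a 45 kg subject is 50/45 - 1 = 11% high, and the 70 kg row for a 65 kg subject is 70/65 - 1 = 7.7% high.
- The excess cannot remove a subject from the per-protocol set.

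All of this stands as a reason to rate the practical effect as small. It does not make the printed figure right. The injection instructions point to the appendices, and the visit steps in Protocol 9.1.2 and 9.1.4 describe the IWRS connection as supplying the box number; it is the SAP that says the IWRS gave the dose. Where the table and the IWRS disagree, staff hold two conflicting figures. If the table were followed, the difference would need a reason in the eCRF and would appear in the compliance description.

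**Conclusion.** The concern holds. The pound entry for 130 kg is wrong in both appendices and should be 286. The error is certain from the tables alone; that it arose from swapped digits is an inference.

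The effect is conditional and small: an excess of 6.7 to 6.9% of either agent for a 268 lb subject dosed by the pound column, less for weights interpolated between 268 and 308 lb, and none for anyone working in kilograms, by the mL/kg rate or from the IWRS volume. The range reflects only the choice between 2.2 and the assumed exact factor. No overdose limit, listed volume deviation, analysis set or primary result is affected. It is a minor correction, worth making because the figure sits in a dosing table that the protocol tells staff to use.

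**What to change.** Change 268 to 286 in the 130 kg row of Appendix 19.1 and of Appendix 19.2. Leave every kilogram and millilitre entry as it is. The cost is one cell in each of two tables; design, sample size and analysis do not change.
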